**Biopsy of ethmoid sinus tissue (for subjects enrolled at the UT Houston site)**

As a part of medically indicated sinus surgery, diseased ethmoid sinonal tissue is removed and a small amount of this tissue will be collected for microarray analysis. The remainder of the tissue will be sent to pathology per routine.

At the time of nasal polyp recurrence or at post-treatment week 24, a small biopsy of ethmoid sinus tissue will be collected. First the site will be topically anesthetized by spraying the nasal and sinus cavity with 1% lidocaine. This is typically done prior to nasal endoscopy which all CRS patients undergo during routine clinic visit. Then, a lidocaine soaked cotton ball will be applied to the biopsy site which will be the posterior medial wall of maxillary antrostomy, for about 5 minutes. After that elapsed time period, endoscopic thru-cutting instrument will be used to obtain a biopsy of ethmoid sinus tissue, approximately 3 mm squared area. Topical afrin will be applied to biopsy site for hemostasis. The collected tissue will be stored at -80C and processed to extract RNA for microarray analysis.

In addition, a swab of the sinuses will be collected and processed for PCR analysis to quantitate and speciate fungal microbiome after treatment.

**Possible Risks to Subjects**

Specific to this study, there are potential risk associated with peripheral blood draws, itraconazole use and biopsy of ethmoid tissue at end of treatment.

**Risk associated with the blood draw**

The main risk associated with the phlebotomy includes discomfort by the needle stick. The amount of blood requested, no more than 50 cc at any one draw, is small and is not associated with anemia or hypovolemia.

**Risk associated with itraconazole, an oral anti-fungal**

Itraconazole is an oral anti-fungal introduced in 1984 that has been utilized in a number of different reported retrospective studies and clinical trials. The FDA has a boxed warning for cardiac effects and drug interactions. From these studies, no serious adverse events were reported with approximately 10% reporting side effects with an incidence no higher than 11% (nausea). Patients experiencing any intolerable side effects may choose to withdraw from the study. Itraconazole is metabolized in the liver and as such patients will be screened for a history of impaired hepatic function.

Patients will be excluded for concomitant use of drugs considered to be contraindicated with the use of Itraconazole. These drugs are:

- a. quinidine (such as Cardioquin® , Quinaglute® , Quinidex® ) .
- b. dofetilide (such as Tikosyn™) .
- c. cisapride (such as Propulsid® ) .
- d. pimozide (such as Orap® ) .
- e. methadone (such as Dolophine® ) .
- f. disopyramide (such as Norpace® ) .
- g. dronedarone (such as Multaq® ) .
- h. ranolazine (such as Ranexa® ) .
- i. lovastatin (such as Mevacor® , Advicor® , Altocor™)
- j. simvastatin (such as Zocor® )
- k. triazolam (such as Halcion® )

- I. midazolam (such as Versed®) ·
- m. lurasidone (such as Latuda®) ·
- n. nisoldipine (such as Sular®) ·
- o. felodipine (such as Plendil®) ·
- p. ergot alkaloids (such as Migranal®, Ergonovine, Cafergot®, Methergine®) ·
- q. eplerenone (such as Inspira®) ·
- r. irinotecan (such as Camptosar®) ·
- s. colchicine (such as Colcrys™) [if you also have pre-existing kidney or liver impairment]

Patients will be screened at each study visit for impaired liver function by asking about symptoms of nausea, vomiting, abdominal pain, swelling of the feet or yellowing of the eyes and skin. Baseline hepatic function will be determined via bloodwork and those with elevated levels will be excluded from the study. Cardiac changes will be monitored at each study clinic visit by asking questions specifically about history of orthopnea, paroxysmal nocturnal dyspnea, dyspnea on exertion with routine activities and changes in exercise tolerance over the treatment course. EKG changes from baseline as defined below will be stopped on study medication.

- 1) Use a QTc interval of 470 ms (males) and 480 ms (females) as the upper limit of normal.
- 2) Discontinue the medication if the QTc > 500 or if it increases by more than 60 ms from baseline.
- 3) Federicia formula to calculate the Qtc ( $QTc = QT/(RR)^{1/3}$ ) will be used
- 4) Patients that have a QTc > 470 (male) or > 480 (female) but still < 500, ECG recheck after 4 half-lives (10 days). If the QTc meets any of the exclusion criteria then they are excluded from the study. If the Qtc remains acceptable then recheck at 1 month.

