This study is a **randomized control trial**, in which patients and treating physicians will be blinded, designed to test whether itraconazole after surgery in fungal sensitive, fungal culture positive CRSwNP patients will have decreased rates of nasal polyp recurrence as compared to placebo treated patients (Figure 1). **The study population will come from the rhinology practice of the Department of Otorhinolaryngology where 3 rhinologists practice** (Drs. [name], [name], and [name]) as well as the rhinology practices at UTSW and UTSA. Among the 3 rhinologists of UT Houston, approximately 150 sinus surgeries are scheduled annually involving CRSwNP. Definitions of CRSwNP are based on the criteria outlined by The Rhinosinusitis Initiative[6]. Inclusion and exclusion criteria are listed in Table 1. Up to 500 CRSwNP patients undergoing a medically-indicated sinus surgery over 3-4 years will be screened and recruited to undergo peripheral blood draw that will be used in an *in vitro* ELISpot assay to identify those that are fungal sensitive. Blood from UTSA and UTSW will be shipped to UT Houston for processing. We anticipate that 80% of those screened patients will meet inclusion criteria allowing us to enroll about 400 CRSwNP patients undergoing sinus surgery. After surgery, patients will be randomized into 1 of 2 groups (1:1 ratio, stratified by presence of asthma): 1) oral itraconazole (200 mg q12 hrs) or 2) placebo for 24 weeks. Patients will be evaluated in the clinic on post-treatment weeks 2 ( $\pm$  1 week), 6 ( $\pm$  2 weeks), 12 ( $\pm$  2 weeks), and 24 ( $\pm$  3 weeks) as per the typical post-operative management protocol (Figure 2). Patients will be clinically followed for an additional 24 weeks post-treatment for recurrent nasal polyps. Therefore, patients will be followed for a total of 48 weeks after sinus surgery or until recurrent nasal polyps requiring treatment are noted.

It is current standard practice for all CRS patients to complete validated health assessment questionnaires for CRS (SNOT-22) and undergo recorded nasal endoscopic exams at each clinic visit. All medications and any treatment side effects will be recorded at each clinic visit.

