**Randomized into itraconazole versus placebo group**

Patients with positive ELISpot assay (indicating fungal immune sensitivity) will be stratified based on asthma and randomized as described above. The Hope Compounding Pharmacy will distribute the appropriate drug to patients in 30-day supply boxed in de-identified pills. The patient randomization list will be kept stored and secured within the Otorhinolaryngology research offices.

Itraconazole is an oral antifungal that can cause adverse reactions. Itraconazole is clinically used routinely for treatment of nail fungus and other fungal diseases. All enrolled patients will be asked about history of congestive heart failure, liver disease, alcohol consumption history, shortness of breath, skin reactions, hearing loss, nerve pain, nausea, vomiting, diarrhea, headaches, chest pain, current medications and any psychological symptoms. In addition, liver function will be measured at baseline before subjects begin their treatment course. With itraconazole, the FDA only recommends routine liver function monitoring in patients with preexisting hepatic function abnormalities. Patients with hepatic disease or elevated liver enzymes at baseline will be excluded from the study.

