**Monitored post-operative by nasal endoscopy, subjective symptoms, adverse reactions, and collection of ethmoid tissue**

As noted in Figure 2, patients will be seen for routine post-operative clinic visits as per typical post-operative standardized care. During these clinic visits, patients routinely undergo review of sinus symptoms, health, medication, and nasal endoscopy and complete health assessment questionnaires. In addition, patients will be asked about any specific adverse events commonly associated with itraconazole as noted above.

For those noted to have recurrent nasal polyps requiring medical intervention, a small biopsy of ethmoid diseased sinusal polyp mucosa will be obtained and stored at -80C for microarray analysis.

For those without recurrent nasal polyps, a small biopsy of ethmoid sinusal mucosa will be obtained and stored at -80C for microarray analysis at post-treatment week 24.

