#### **Data and Safety Monitoring**

A Data Safety Monitoring Board will be established and chaired by [name] (Pediatric Allergist). In addition, other members of the Board will consist of [name] (anesthesiologist and member of IRB) and [name] (Director of the Laboratory of Mycology Research). This committee will meet at the beginning of the study and regularly throughout the duration of the clinical trial to oversee the progress of the trial including any adverse events and to ensure patient safety. Any adverse events occurring during the duration of the study will be recorded on the patient's data sheets. If the adverse event such as bleeding is controlled, the subject will be offered the opportunity to continue or discontinue involvement in the study. They will be promptly reported to the CPHS according to the established protocol. Again, subjects may opt to discontinue involvement of the study at any time. The CPHS will be updated to the progress of the study per established protocol.

If at any time >5% of the study population experiences a serious adverse reaction, the study will be stopped until the Data Safety Monitoring Board has time to convene and discuss the event and safety of the trial.

Given minimal adverse events with study drug and additional documentation from other larger clinical trials using oral itraconazole, the protocol was changed and approved such that hepatic function only needed to be checked at the beginning of the trial and monitored via symptoms and cardiac function was monitored with EKG and symptoms. As such, the DSMB with outside expertise on possible itraconazole adverse events seemed unnecessary. In its place, Drs. [name], [name] and [name] meet monthly to review all active trials and research projects associated with the rhinology group. At this meeting, any adverse events or irregularities with the trial will be reviewed and documented.

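### After baseline the liver is followed by symptom questions alone, and the plan ties no repeat panel or drug decision to a positive answer

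*Combined protocol and SAP*

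**What the plan says.** The document is the combined protocol and SAP.

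- **Testing.** A hepatic panel is required before treatment, and raised enzymes exclude the patient. *Data and Safety Monitoring* then records a change under which "hepatic function only needed to be checked at the beginning of the trial and monitored via symptoms". The extra week 24 vial in *Peripheral Blood Draw* is for inflammatory markers.
- **Screening on treatment.** Under *Risk associated with itraconazole, an oral anti-fungal*, patients are screened at each visit "for impaired liver function by asking about symptoms of nausea, vomiting, abdominal pain, swelling of the feet or yellowing of the eyes and skin". The post-operative monitoring section adds that "patients will be asked about any specific adverse events commonly associated with itraconazole as noted above".
- **Reason given.** *Randomized into itraconazole versus placebo group* states: "With itraconazole, the FDA only recommends routine liver function monitoring in patients with preexisting hepatic function abnormalities". *Data and Safety Monitoring* adds that few adverse events had been seen and that larger trials were available.
- **Recording.** *Study Design*: "All medications and any treatment side effects will be recorded at each clinic visit". Events are also reported to the CPHS and reviewed at a monthly physician meeting.
- **Exits.** "Patients experiencing any intolerable side effects may choose to withdraw from the study". Once an event is controlled, "the subject will be offered the opportunity to continue or discontinue involvement in the study". *Patient Withdrawal from Study* says that investigators can withdraw a patient who has complications from the medication or who meets an exclusion criterion.
- **Visits and dose.** "Patients will be evaluated in the clinic on post-treatment weeks 2" (±1 week), then 6 (±2), 12 (±2) and 24 (±3). The dose is 200 mg every 12 hours for 24 weeks.

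**The concern.** Once blood tests stop, the symptom questions are the only liver safeguard the plan specifies, for 24 weeks at 400 mg a day. A screen needs a stated consequence, and this one has none. Two patients who give the same answer at different sites can be handled in opposite ways, one kept on drug untested and the other stopped, and both would be within protocol.

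There is also a statistical stake. *Patient Withdrawal from Study* treats a drug complication as grounds for leaving the study, not only for stopping the drug. A patient removed that way may not contribute the 48-week recurrence endpoint. If complications are more common on itraconazole, such losses would fall unevenly between the arms. The documents give no rates by arm, so the size of this cannot be stated.

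**Working it through.** The plan states no figure on this point, so there is nothing to reproduce. The check is mainly a comparison of provisions.

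**1. Where hepatic panels appear.** They are named in *Study Design*, *Study Population*, *Peripheral Blood Draw*, *Randomized into itraconazole versus placebo group*, *Risk associated with itraconazole* and *Data and Safety Monitoring*. Each time the test is at baseline. Panels specified after baseline, scheduled or prompted by symptoms: 0.

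**2. What follows a positive answer.**
- Patient's choice to withdraw: permissive, with no test attached.
- Investigator's option to withdraw: permissive. The laboratory exclusion is for enzymes raised at baseline. Without a later panel, a new elevation would not be known.
- Offer to continue or stop: applies once an event is controlled, and carries no hepatic criterion.
- Safety endpoint in *Study Design*: counts patients whose side effects force them off the drug, but does not say when that should happen.
- Trial-level pause at more than 5% serious reactions: 0.05 × 120 = 6 and 0.05 × 400 = 20, so it needs more than 6 or more than 20 patients. It does not direct the care of one patient.

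**3. Comparison within the same section.** The QTc has upper limits of 470 and 480 ms. Drug must be stopped above 500 ms or after a rise of more than 60 ms, and intermediate values are rechecked at 10 days and again at 1 month. The liver has no counterpart.

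**4. When a rule could act.** Visit weeks are read as weeks from the start of treatment (an assumption). Drug remaining at nominal visit times:
- Week 2: 24 − 2 = 22 weeks
- Week 6: 24 − 6 = 18 weeks
- Week 12: 24 − 12 = 12 weeks
- Week 24: 24 − 24 = 0. The window opens at 24 − 3 = week 21, so up to 24 − 21 = 3 weeks of drug may remain, and this visit can be a fourth opportunity.

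The nominal wait until the next scheduled question is 6 − 2 = 4, 12 − 6 = 6 and 24 − 12 = 12 weeks. These waits come from the visit schedule, which the fix leaves alone. They describe the setting and do not measure the benefit.

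**5. Extra panels for nausea alone, itraconazole arm.** The risk section gives about 10% for side effects overall and at most 11% for nausea in previous studies. Arm sizes at 1:1 are 400 / 2 = 200 (from the enrolment of about 400 in *Study Design*) and 120 / 2 = 60 (the low scenario in *Power analysis*). Assume that the rate applies here and that every case is new and persistent:
- 0.11 × 200 = 22; 0.11 × 60 = 6.6, about 7
- 0.10 × 200 = 20; 0.10 × 60 = 6

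Vomiting, abdominal pain, jaundice, foot swelling and the whole placebo arm come on top. The documents give no rate for any of them.

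**The case against.** The strongest reply is that this is ordinary clinical care. Physicians see these patients in clinic, the questions are asked expressly to detect liver impairment, and patients with liver disease or raised enzymes never enter. Nothing forbids an unscheduled panel, and jaundice can be recognised on examination. All of that is true, and it limits the severity. It does not supply the missing instruction, and the sponsor did not leave the QTc to judgement in the same section.

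Several stronger readings are tempting, and the documents do not support them:

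- *Routine panels should be restored.* The plan explains why they were dropped. That reason concerns routine monitoring and is silent on a patient with symptoms, so only the symptomatic patient is at issue here.
- *Liver symptoms go undocumented.* They are recorded at visits, reported and reviewed. What is missing is the trigger and the criterion.
- *Every exit in the trial is discretionary.* This holds for the liver only; the QTc stop is mandatory.
- *Anyone stopped for a liver reason is lost to the primary endpoint.* The safety endpoint and the EKG rule both recognise stopping drug as separate from leaving the study. The loss is allowed by *Patient Withdrawal from Study* but not required.
- *The nausea count caps the number of extra panels.* It covers one symptom in one arm.

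**Conclusion.** The concern holds in this form: after baseline the liver is followed by symptom questions alone, a positive answer prompts no panel and no drug decision, and the applicable exits are discretionary. The plan should be changed. A patient with persistent symptoms can remain on drug untested for up to 22 further weeks from the nominal week 2 visit without any deviation. The rates of liver symptoms and liver injury in this trial are not in the documents, so no number of patients harmed is claimed. The conclusion rests on the text. The arithmetic only shows when a rule could act and roughly what part of it would cost.

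**What to change.** Add to *Risk associated with itraconazole, an oral anti-fungal*, identically in both arms and for the 24-week course:

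1. New jaundice, or persistent vomiting or abdominal pain: hold study drug, repeat the baseline hepatic panel, and document a decision to resume or stop.
2. New persistent nausea alone, or new foot swelling: repeat the panel and continue drug unless the panel is raised. Foot swelling also calls for the cardiac questions.
3. The sponsor fixes the enzyme and bilirubin limits, and the meaning of persistent, in advance and once for all three sites.

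State in *Patient Withdrawal from Study* that a patient stopped for a liver reason or another drug complication stops study drug but stays in follow-up for the 48-week endpoint unless consent is withdrawn.

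The cost is one amendment and unscheduled repeats of a panel already in use. Their total number cannot be given, because only the nausea part can be sized. There is also a small risk that a raised panel hints at allocation to the blinded treating physician, who decides on prednisone for recurrence and so influences the primary endpoint.

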## **Study Procedures**

### EKG

Enrolled patients who respond negative to all screening questions about ventricular dysfunction will undergo a baseline EKG. Only those patients with normal EKGs, no evidence of ST changes or prolonged Q-T interval, will be able to participate in the study. The EKG will be performed before any study medication is dispensed.

A baseline EKG will be required. A follow-up EKG will be performed at each follow up visit.

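### QTc items 2 and 4 overlap with no stated precedence, and item 4 leaves the study-drug status, the exclusion criteria and the final outcome open

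*Combined protocol and SAP*

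**What the plan says.** The rules are four numbered items at the end of the section on risk associated with itraconazole. The sentence before them says "EKG changes from baseline as defined below will be stopped on study medication".

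- Item 1 sets a limit and attaches no action: "Use a QTc interval of 470 ms (males) and 480 ms (females) as the upper limit of normal".
- Item 2 is the stopping rule: "Discontinue the medication if the QTc > 500 or if it increases by more than 60 ms from baseline".
- Item 3 names the correction formula.
- Item 4 begins "Patients that have a QTc > 470 (male) or > 480 (female) but still < 500, ECG recheck after 4 half-lives (10 days". It continues "If the QTc meets any of the exclusion criteria then they are excluded from the study" and ends "If the Qtc remains acceptable then recheck at 1 month".

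Four other places bear on these items. Under Study Procedures, the EKG section sets entry, "Only those patients with normal EKGs, no evidence of ST changes or prolonged Q-T interval, will be able to participate in the study", and the on-study schedule, "A follow-up EKG will be performed at each follow up visit". The exclusion list under Study Population also rules out known EKG abnormalities. Study Design places visits at weeks 2 (±1), 6 (±2), 12 (±2) and 24 (±3), with follow-up to 48 weeks. Patient Withdrawal from Study lets investigators withdraw a patient who has complications from the medication, but does not require it.

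**The concern.** A safety rule should give each EKG reading one action. Items 2 and 4 use different scales. Item 2 uses an absolute value or a change from baseline, and item 4 uses an absolute band only. Nothing says how they combine. Three sites following the text exactly could stop the drug, recheck first, or later exclude the same patient from the study.

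EKG change is a listed safety endpoint under Study endpoints, and the risk section cites a boxed warning for cardiac effects. The Data and Safety Monitoring section also points to EKG and symptom monitoring when it explains why a board with outside expertise was no longer thought necessary, so these items carry real weight. Part of the discontinuation and EKG data would depend on how a site reads them. A normal recheck could not be interpreted without knowing whether the patient was on drug. Stopping medication and leaving the study also differ for the 48-week endpoint: the first can keep the patient in follow-up, and the second appears to end it.

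**Working it through.** **Overlap of items 2 and 4.** Let B be baseline QTc, Q the on-drug QTc, and L the upper limit in item 1 (470 ms men, 480 ms women). Item 2 applies if Q > 500 or Q − B > 60. Item 4 applies if L < Q < 500. Crossing the two gives:

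| Q | Q − B | Item 2 | Item 4 | Example (man) |
|---|---|---|---|---|
| at or below L | 60 or less | no | no | – |
| at or below L | above 60 | stop | no | 400 to 465 (+65) |
| above L, below 500 | 60 or less | no | recheck | 430 to 475 (+45) |
| above L, below 500 | above 60 | stop | recheck | 405 to 475 (+70) |
| exactly 500 | 60 or less | no | no | 450 to 500 (+50) |
| exactly 500 | above 60 | stop | no | 430 to 500 (+70) |
| above 500 | any | stop | no | 450 to 505 (+55) |

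The fourth row is the overlap. It needs B < Q − 60 with Q < 500, so B < 440 ms for both sexes. In whole milliseconds the limit is B below 439, because 499 − 439 = 60 is not above 60. The whole item 4 band overlaps when B is at or below 470 − 60 = 410 (men) or 480 − 60 = 420 (women). Between those values and 440 only the upper part of the band overlaps. For a man at 425, for example, 471–485 is recheck only and 486–499 meets both items. A woman going from 420 to 485 (+65) also meets both.

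The fifth row is a gap: exactly 500 ms with B at 440 or above has no action.

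**Drug status until the recheck.** The plan equates 4 half-lives with 10 days, so the implied half-life is 10/4 = 2.5 days. Under first-order elimination with drug held, the fraction left at the recheck is 0.5^4 = 0.0625, about 6%. With drug continued there is no washout. The same normal reading would mean recovery off drug in one case and an acceptable QTc under exposure in the other.

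**The unnamed exclusion criteria.** Take a man who goes from 430 to 475 ms and is still at 475 at the recheck (+45).

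- If the criteria are those of item 2, he meets none (475 is not above 500, and 45 is not above 60), so he is acceptable and rechecked at 1 month.
- If they are the entry criteria under Study Population and EKG, he is above the 470 ms limit of normal, so he is excluded.

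**EKGs after a stop.** Within items 1–4, a stop in the second, sixth or seventh row carries no dedicated recheck. The next required EKG is at the next scheduled visit. The longest gap is (later visit + window) − (earlier visit − window):

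- weeks 2 to 6: (6 + 2) − (2 − 1) = 7 weeks
- weeks 6 to 12: (12 + 2) − (6 − 2) = 10 weeks
- weeks 12 to 24: (24 + 3) − (12 − 2) = 17 weeks

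Nominal gaps are 4, 6 and 12 weeks. A patient in item 4's band has a recheck at 10 days.

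**The case against.** The strongest reply is that the items overlap but do not strictly contradict each other. Item 2 is unconditional, item 4 never tells a site to continue the drug, and a site could stop and recheck together. That is fair, and the point is put here as an overlap with no precedence. It does not remove the problem, because the text does not say to do both and item 4 adds a different end, exclusion from the study.

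A reader might infer that patients stopped for the largest QTc changes get no further EKG. The documents do not support that. The EKG section requires one at each follow-up visit with no exemption for patients off drug, and item 4 also rechecks stopped patients inside its band. Only the absence of a dedicated, timed recheck outside that band stands. It matters most between weeks 12 and 24, and the visit EKG depends on the patient not being withdrawn.

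A reader might also take the introductory sentence to mean that anyone above item 1's limit must be stopped. That is strained: the sentence concerns changes from baseline, and item 1 defines a limit with no action.

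The gap at exactly 500 ms is minor and arises only with a rise of 60 ms or less.

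**Conclusion.** The concern holds in this form. For baselines below 440 ms in either sex, items 2 and 4 can both apply with no rule on which governs. At or below 410 ms (men) or 420 ms (women), every reading in item 4's band meets both. Drug status before the recheck, the exclusion criteria meant, and whether the patient leaves treatment or the study are all left open. These follow from the text alone. The 6% figure rests on first-order kinetics and the plan's own equation of 4 half-lives with 10 days. The 17 weeks assumes that visits fall at opposite ends of their windows.

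Two larger conclusions are not supported. One is that discontinuation counts depend on the reading and not on the drug: stops above 500 ms are explicit, so only part of the data is affected. The other is that the polyp-recurrence comparison is biased: the documents give no QTc distribution, so the number of patients affected is unknown, and no effect on the primary endpoint is shown.

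**What to change.** Reconcile items 1–4 and their introductory sentence with the Study Population exclusions, the EKG section and Patient Withdrawal from Study, as one set of QTc categories that do not overlap, leave no value out (including exactly 500 ms), and carry one action each. The amended text should:

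- state which item governs when items 2 and 4 both apply;
- name the criteria meant by item 4's reference to exclusion criteria;
- state the study-drug status until the recheck;
- say whether the patient leaves treatment only or the study, and so whether 48-week follow-up continues;
- say how a stop under item 2 relates to the visit EKG schedule.

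The actions are for the sponsor's clinical advisers to choose; none is proposed here. The cost is a one-paragraph amendment and a notice to the three sites. Sample size and the primary analysis are unaffected.
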